The first three cases at each institution (baseline and at least one follow-up) will be performed under the guidance of at least one of the study PIs to ensure standardization amongst all three sites. The ultrasound examinations will be performed by a qualified sonographer. Efforts will be made to have all CEUS scans performed by the same dedicated sonographer, enabling us to evaluate operator dependence. During the ultrasound examination, the patient will be asked to lie in the supine position and a 20-22 gauge cannula will be placed in a superficial vein (preferably an antecubital vein). Ultrasound imaging will be performed using a state of the art Logiq E9 scanner with C1-5-D broad-spectrum convex transducer and a RAB2-5-D broad-spectrum real-time 4D transducer (GE Healthcare, Wauwatosa, WI). As part of this study, we have budgeted for the purchase of 3 4D probes (not routinely available in clinical practice) and the installation of GE's ultrasound volumetric and contrast imaging packages that provide 2D and 4D CEUS capabilities. In the event the patient has multiple lesions scheduled for treatment, up to 2 lesions will be imaged independently on CEUS. Patients will first undergo 2D baseline imaging. B-mode measurements and sweeps of the lesion in the transverse and sagittal planes will be performed, followed by standard power Doppler imaging (PDI). Following baseline imaging, patients will receive a bolus IV injection of up to 0.6 ml of Definity, followed by a 10 cc saline flush. Since Definity is currently only approved for echocardiography, we will apply to the FDA for an investigational new drug application for CEUS evaluation of TACE (similar to our previous study [Shaw et al. 2014]).

All CEUS imaging will be performed using the dual B-mode (used to locate anatomical features) and

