reader. Studies will be presented in random order. The second round reads will be performed at least one month after the first. Outcomes will be defined as incompletely treated (i.e. requiring retreatment) based on (in order of preference of reference standard): a) pathological examination of explanted livers demonstrating live tumors; b) tumor enhancement seen with CT or MR and confirmed via angiography during retreatment; c) tumor growth on 6 month follow-up CE-CT/MRI; or d) asymmetrical or nodular tumor enhancement on CE-MRI/CT on 6 month follow-up. Incomplete treatment on CEUS (2D or 4D) will be evaluated by each reader and evidenced by the tumor showing either residual blood flow after treatment or nodular peripheral blood flow.

For questions 1-2, sensitivity (the ability to detect patients in need of retreatment) and specificity (the ability to identify patients who do not require retreatment) will first be calculated on a reader by reader basis. Four 2 x 2 tables will be constructed comparing the need for re-treatment based on the clinical gold standard described above and CEUS, tabulating true positives, false positives, false negatives, and true negatives. A table will be created for CEUS at 1-2 weeks and 1 month for both 2D and 4D CEUS and used to calculate sensitivity, specificity, accuracy, positive predictive value, and negative predictive value. Statistical significance between the reference standard and each of the 4 CEUS groups will be determined using a McNemar test. These values will also be calculated based on the majority decision (i.e. 4 or more readers in agreement). In the event of discordant readings during this analysis, tumor outcome will be decided by consensus by the two readers at TJU. Differences between techniques (2D vs. 4D) and time points (1-2 weeks vs. 1 month post treatment) will be determined by comparing areas under the receiver operating characteristic curves for each modality/time point based on necessity of tumor retreatment. Intra-rater and inter-rater variability will be calculated using a Shrout and Fleiss Interclass Correlation [Shrout and Fleiss 1979]. Finally, a logistical regression and analysis of variance will be performed to determine if significant variations exist between individual sites (to determine operator dependence), lesion size (tumor size dependency) or between patients treated with cTACE vs. DEB-TACE (treatment dependency).

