For statistical question 3, all quantitative parameters will be compared between fully treated and incompletely treated masses using a Student's t-test. Additionally, lesions that demonstrate lack of residual enhancement at 1 month, but show recurrence at 6 month follow-up, will be compared to completely treated masses to determine if quantitative CEUS parameters can detect this lower level of residual disease. Statistical analysis will be performed with assistance from the biostatistician co-investigator using Stata 12.0 (Stata Corp, College Station, TX) with p values < 0.05 considered statistically significant after a Bonferroni-type adjustment for multiple tests. These statistical tests will answer our three major questions regarding the sensitivity and specificity of 2D and 4D CEUS as an imaging tool for the follow-up of TACE

at 1-2 weeks and 1 month (specific aims 1-2), as well as the influence of operator, reader, tumor size, and embolization material.

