7.2.1 Sample Size Justification

As the most clinically important aims, aims 1-2 will be used as the basis for the sample size analysis, where each patient represents an independent data point used to evaluate the technique's sensitivity and specificity at both 1-2 weeks and 1 month follow-up times. Based on our pilot studies using 2D CEUS to evaluate TACE performed using Lipiodol [Kono et al. 2007] or drug-eluting-beads [Shaw et al. 2014], we expect to encounter a patient population in which up to 67% of patients require retreatment. A sample size analysis was performed using a binomial test with One-Sample Sensitivity and Specificity Analysis in NCSS/PASS 2008 (NCSS, East Kaysville, UT) to estimate the number of cases required to produce a over 85% power for this study. This analysis assumes sensitivity and specificities of 98%, an alpha of 0.05, prevalence of disease of 66.7%, and null sensitivity and specificities of 90%. Results from this analysis are provided in tabular format below.

Preva- ---- Power ----		Sample	--- Sensitivity ---		--- Specificity ---		----- Alpha -----			P
Size	H0 Sens. Spec.	H1 N1 and N	H0 Se0	H1 Se1	Sp0	Sens. Sp1	Spec. Target	lence Actual	Actual	P
0.0000	0.0000	7								
10	0.9000	0.9800	0.9000	0.9800	0.0500	0.0000	0.0000	0.6670		
0.0000	0.0000	13								
20	0.9000	0.9800	0.9000	0.9800	0.0500	0.0000	0.0000	0.6670		
0.0000	0.0000	20								
30	0.9000	0.9800	0.9000	0.9800	0.0500	0.0000	0.0000	0.6670		
0.0000	0.0000	27								
40	0.9000	0.9800	0.9000	0.9800	0.0500	0.0000	0.0000	0.6670		
0.5134	0.0000	33								
50	0.9000	0.9800	0.9000	0.9800	0.0500	0.0309	0.0000	0.6670		
0.4457	0.0000	40								
60	0.9000	0.9800	0.9000	0.9800	0.0500	0.0148	0.0000	0.6670		
0.7581	0.0000	47								
70	0.9000	0.9800	0.9000	0.9800	0.0500	0.0440	0.0000	0.6670		
0.7135	0.0000	53								
80	0.9000	0.9800	0.9000	0.9800	0.0500	0.0259	0.0000	0.6670		
0.6619	0.5455	60								
90	0.9000	0.9800	0.9000	0.9800	0.0500	0.0138	0.0424	0.6670		
0.8494	0.5134	67								
100	0.9000	0.9800	0.9000	0.9800	0.0500	0.0307	0.0309	0.6670		
0.8202	0.4735	73								
110	0.9000	0.9800	0.9000	0.9800	0.0500	0.0190	0.0203	0.6670		
0.9231	0.4457	80								
120	0.9000	0.9800	0.9000	0.9800	0.0500	0.0353	0.0148	0.6670		
0.9027	0.4195	87								
130	0.9000	0.9800	0.9000	0.9800	0.0500	0.0211	0.0108	0.6670		
0.9608	0.7581	93								
140	0.9000	0.9800	0.9000	0.9800	0.0500	0.0382	0.0440	0.6670		

0.9492	0.7358	100							
150	0.9000	0.9800	0.9000	0.9800	0.0500	0.0237	0.0338	0.6670	

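### Up to two lesions per patient may be imaged, but the question 3 t-test makes no allowance for within-patient correlation, and no rule says which lesion represents the patient in the sensitivity and specificity tables

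*Combined protocol and SAP*

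**What the plan says.** - **Imaging.** Synopsis, Trial Procedures, for a patient with more than one lesion due for treatment: "up to 2 lesions will be imaged independently on CEUS".
- **Question 3 (secondary aim).** Section 7.2: "all quantitative parameters will be compared between fully treated and incompletely treated masses using a Student's t-test". A further comparison follows: "lesions that demonstrate lack of residual enhancement at 1 month, but show recurrence at 6 month follow-up, will be compared to completely treated masses". Neither sentence contains a patient-level term.
- **Questions 1-2 (primary objective).** Section 7.2 defines both measures by patient; specificity, for instance, is "the ability to identify patients who do not require retreatment". The same section speaks of a tumor outcome when it settles discordant reads, and reference criteria a) to d) describe findings in tumors.
- **Sample size.** Section 7.2.1 states that "aims 1-2 will be used as the basis for the sample size analysis" and that "each patient represents an independent data point". It counts 201 patients. Question 3 has no sample size.
- **Not found in the protocol or SAP text.** A mixed model, generalized estimating equations, a clustered variance, an index lesion, or a rule for a patient whose two lesions have different outcomes.

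**The concern.** Two lesions in one patient share a liver and an imaging session, so their perfusion parameters may well be correlated. A Student's t-test assumes independent observations. If both lesions enter it, its standard error is computed under an assumption that the design breaks, and a biomarker may be declared significant, or missed, for that reason alone. The Bonferroni-type adjustment in section 7.2 does not help: it lowers the threshold for the number of tests and leaves the standard error as it is.

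For questions 1-2 the exposure is different. The tables are per patient, but a patient with two imaged lesions can have one fully treated and one not, or one CEUS-positive and one CEUS-negative. Without a rule, someone must choose a lesion or a way of combining the two, possibly after the reads are known.

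**Working it through.** **1. Reproduce the plan's power (patient as unit).** Inputs from section 7.2.1: null 0.90, alternative 0.98, alpha 0.05, and 133 patients with and 67 without residual disease (the row for 200). The test is an exact binomial; the one-sided version matches the printed table.

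- Sensitivity, n = 133, reject if X ≥ 126: P(X ≥ 126 | 0.90) = 0.0385; P(X ≥ 126 | 0.98) = 0.9945.
- Specificity, n = 67, reject if X ≥ 65: P(X ≥ 65 | 0.90) = 0.0307; P(X ≥ 65 | 0.98) = 0.8494.

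These equal the printed values. With one result per patient, the 99% and 85% stand.

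**2. Design effect if both lesions enter the t-test.** Let f be the share of patients with two analyzed lesions and ρ the within-patient correlation of the parameter. The documents give neither, so both are assumed over a range. With 201 patients there are 201(1+f) lesions, and a fraction 2f/(1+f) of them belong to pairs. When both lesions of a pair fall in the same outcome group:

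DE = 1 + ρ·2f/(1+f); true SE / naive SE = √DE; actual two-sided error ≈ 2Φ(−1.96/√DE).

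Example, f = 0.3 and ρ = 0.5: lesions = 201 × 1.3 ≈ 261; DE = 1 + 0.5 × 0.6/1.3 = 1.23; √DE = 1.11; error = 2Φ(−1.96/1.109) = 7.7%; effective number of lesions = 261/1.231 ≈ 212.

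| f | ρ | lesions | DE | SE ratio | error at nominal 5% |
|---|---|---|---|---|---|
| 0.2 | 0.3 | 241 | 1.10 | 1.05 | 6.2% |
| 0.2 | 0.7 | 241 | 1.23 | 1.11 | 7.8% |
| 0.3 | 0.5 | 261 | 1.23 | 1.11 | 7.7% |
| 0.5 | 0.3 | 302 | 1.20 | 1.10 | 7.4% |
| 0.5 | 0.7 | 302 | 1.47 | 1.21 | 10.6% |

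**3. Dependence on the outcomes of the pair.** The formula covers only concordant pairs. The ordinary t-test was therefore simulated with 201 patients, 66.7% of lesions incompletely treated, a patient random effect, no true group difference and 4,000 runs per setting. Monte Carlo standard error near 5% is √(0.05 × 0.95/4000) ≈ 0.3 percentage points.

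| Outcomes of the two lesions | error, f = 0.3, ρ = 0.5 | SE ratio, same setting | error over f 0.2–0.5, ρ 0.3–0.7 |
|---|---|---|---|
| Always the same | 8.0% | 1.11 | about 6% to 10.5% |
| Same with weight 0.5, otherwise independent | 6.8% | 1.07 | about 5% to 7.5% |
| Independent | 4.6% | 0.99 | about 5% |
| Always different | 2.2% | 0.87 | 1.6% to 3.3% (f = 0.3 only) |

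So the direction is not fixed. The naive standard error is too small when both the parameter and the outcome are positively correlated within a patient, about right when outcomes are independent, and too large when pairs are split between the groups.

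**The case against.** The strongest counter-argument is that the plan may intend one mass per patient throughout. The two-lesion sentence stands only in the synopsis. Section 6.3 describes the same procedure without it and speaks of a single lesion. Sections 6.5 and 7.2 have readers locate one treated mass, and the 201 cases they read equal the 201 patients analyzed. The plurals in the question 3 text are also what one would write with one mass in each of many patients. This stands in part: that both lesions enter the t-test is an inference. It does not remove the problem, because the synopsis creates second-lesion data and no text excludes those data from a comparison of masses.

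Three stronger readings are tempting and are not supported.

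- **That the plan declares the two lesions statistically independent, so its standard errors are too small.** The word independently in the synopsis describes how lesions are scanned. The direction of any error depends on the pairs' outcomes, as shown above.
- **That the sensitivity and specificity tables use a different unit from the power calculation.** Sections 7.2 and 7.2.1 both use the patient, and the stated power reproduces exactly. What is missing is a rule for a patient with two lesions.
- **That the specificity power is really lower than 85%.** If a patient counted as CEUS-positive when either lesion was, and 98% held per lesion with independent false positives, then with 30% two-lesion patients the patient-level specificity would be 0.7 × 0.98 + 0.3 × 0.98² = 0.974 and the power 0.749. But the plan states no either-lesion rule and applies 98% to patients. The figure shows only that the choice of rule could matter.

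It is also fair to say that question 3 serves a secondary, developmental aim with no power claim, and that the error rates above are per comparison, before the Bonferroni-type adjustment.

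**Conclusion.** The point holds in a limited form. The plan allows two lesions per patient, specifies for question 3 a test with no allowance for correlation between them, and does not say which lesion represents the patient in questions 1-2. If both lesions are analyzed, the t-test's standard error is unreliable. In the adverse case (concordant outcomes, f 0.2 to 0.5, ρ 0.3 to 0.7) the error is about 6% to 10.5% instead of 5%, with about 8% at f = 0.3 and ρ = 0.5. With independent outcomes it is about nominal, and with discordant pairs the test is conservative. These figures rest wholly on assumed f and ρ; the documents do not allow the actual size to be fixed. The primary power statement is not in question provided each patient contributes one result. The change is worth making because it replaces a stated method with one that is suitable in all of these cases, at little cost.

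**What to change.** 1. **Question 3 and any lesion-level comparison**, including late-recurring lesions against completely treated masses: replace the Student's t-test with a linear mixed model with a patient random effect, or with a regression using patient-clustered standard errors. Either handles concordant and discordant pairs, and patients with one lesion stay in the analysis.
2. **Questions 1-2**: define one index lesion per patient, fixed at baseline before TACE (for example the largest treated lesion), and use it for both the CEUS result and the reference standard. This keeps the patient-level basis of section 7.2.1.
3. State in sections 6.3 and 7.2 how a second lesion is recorded and which analyses it enters, so that they agree with the synopsis. Report how many patients have two analyzed lesions.

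Cost: SAP wording and slightly more analysis, with no added patients or procedures. Intervals for question 3 may be wider, and second lesions contribute only to lesion-level analyses.

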1. INTRODUCTION

Hepatocellular carcinoma (HCC) is the third leading cause of cancer mortality worldwide and the incidence is increasing. While surgical resection and transplantation offer the possibility of long-term cure, the majority of patients are not eligible for these treatments. Transarterial chemoembolization (TACE) is standard of care for patients with Barcelona Clinic Liver Cancer stage B disease but may also be used as bridging therapy in patients who are potential transplant candidates. Current guidelines recommend follow-up imaging 4-6 weeks after all tumor-bearing areas have been treated. Incomplete treatment is defined as persistence of enhancing areas inside the treated lesions seen at the first imaging study after locoregional treatment and is observed in up to two-thirds of patients post TACE. Contrast-enhanced magnetic resonance imaging (CE-MRI) has been established as the clinical standard imaging modality for evaluating treatment

response and contrast-enhanced computed tomography (CE-CT) is used when CE-MRI is contraindicated. However, there are multiple reasons patients may not undergo cross-sectional imaging follow-up - metallic implants, renal impairment, allergies to contrast medium, and anxieties related to confined space or radiation exposure. Additionally, the cost and availability of these techniques are disadvantageous compared to ultrasound imaging.

Contrast-enhanced ultrasound (CEUS) is a well-established technique for enhancing echocardiograms in the United States and is approved for a wide range of vascular and oncologic applications worldwide. These contrast agents function as blood pooling agents and unlike the contrast agents used in MRI/CT, are not nephrotoxic and have no renal contraindications, making them an exceptionally safe imaging agent. Additionally, CEUS imaging is not influenced by residual Ethiodol or post-surgical inflammation in the liver, potentially offering an earlier option for monitoring treatment response of TACE compared to the current clinical standard. In this study, we propose a multi-center clinical trial to determine the sensitivity and specificity of two and real time three-dimensional (2D and 4D, respectively) CEUS for evaluating TACE. In addition, quantitative biomarkers based on parametric imaging will be defined for identifying patients in need of retreatment. These techniques may provide a safer, more accurate imaging alternative for evaluating TACE effectiveness, as well as earlier identification of residual disease requiring retreatment. The multi-center nature of this proposed study allows sufficient sample sizes to define the sensitivity and specificity of CEUS within an adequate confidence interval, as well as investigate its operator and reader dependencies. Once properly validated, this technique is expected to improve patient outcomes by offering a viable imaging alternative in cases where CE-MRI/CT is contraindicated and enabling earlier identification of residual disease in need of retreatment.

1.1 Background

Hepatocellular carcinoma (HCC) is the fifth most prevalent cancer worldwide, with over half a million new cases reported per year [Alterkruse et al. 2009]. The rising incidence of HCC over the last 20 years is primarily attributed to the rise in hepatitis C virus infections [El-Serag and Mason 1999]. Surgery offers the best chance for long term cure; however, only 30% of referred patients are eligible for surgical resection, and this group is still plagued by 5 year recurrence rates higher than 70% [Bruix and Llovet 2002]. Transplantation is another treatment option for HCC, with the 5 year survival rates for liver transplantation at 68%, [Watt et al. 2010] yet is severely limited by tumor burden and the availability of donors [Kim et al. 2013; Llovet et al. 1999].

In patients with unresectable disease, locoregional treatment options include thermal ablation,

radioembolization and transarterial chemoembolization (TACE). Since hepatocellular cancers are almost exclusively supplied by the hepatic arterial system and the liver has a dual blood supply (approximately 75% from the portal vein and 25% from the hepatic artery), trans-arterial treatment of tumors can be performed while limiting toxicity to the surrounding uninvolved parenchyma [Chapman et al. 2008; Gonsalves and Brown, 2009; Bruix and Sherman 2010]. While this technique is primarily used for the treatment of HCC, it has also been successful for a variety of hepatic malignancies [Burger et al. 2005; Herber et al. 2007; Giroux et al. 2004; Brown et al. 2012; Fiorentini et al. 2007; Patel et al. 2005; Sato et al. 2005; Madoff et al 2006].

TACE involves the direct infusion of chemoembolic agents via a catheter placed in the tumor feeding artery [Yamada et al. 1995]. Conventional TACE (cTACE) uses chemotherapeutic agents mixed with Lipiodol, followed by an embolic material. Drug-eluting bead TACE (DEB-TACE) uses chemotherapeutic agents adsorbed onto poly-vinyl alcohol beads. The bead size is standardized and chosen based on tumor size and sub selective vascular access. Regardless of which embolic agents are used, the goal remains the same, to render the tumors ischemic while depositing high doses of chemotherapy in the tumor [Gonsalves and Brown 2009]. Tumor ischemia causes the disruption of intracellular glycoprotein pumps, which inhibits tumor cells from expelling chemotherapeutic agents, resulting in a six-fold increase in drug retention [Sasaki et al. 1987].

During cTACE, iodinated, ester derived poppy-seed oils serve as drug carriers, as temporary embolization material, and as imaging agents under fluoroscopy [Gonsalves and Brown, 2009]. The chemotherapeutic agents used may vary, but most frequently consist of a cisplatin, adriamycin, and mitomycin (CAM) mixture [Van Ha 2009]. Following delivery, more permanent embolization is achieved with materials such as poly-vinyl alcohol or gelfoam [Gonsalves and Brown, 2009]. While cTACE is an effective therapy for slowing disease progression, improved patient responses with less toxicity have been observed with the use of DEB-TACE [Vogl et al. 2011; Lammer et al. 2010; Gaba 2012]. Embolization with DEB-TACE results in occlusion of the tumor vasculature, combined with a sustained, intratumoral release of the chemotherapeutic [Lewis et al. 2006]. Compared with cTACE, DEB-TACE is associated with greater treatment tolerance and significantly less liver toxicity and doxorubicin-related side effects [Vogl et al. 2011, Lammer et al 2010].

Both TACE procedures are performed under fluoroscopic guidance for catheter placement and infusion monitoring, with infusions continuing until near stasis in the tumor-feeding artery is observed [Van Ha 2009]. Access to the tumor vasculature is achieved via a catheter placed in the hepatic artery. Technical

success, defined as correct catheter placement and drug administration, is achieved in approximately 98% of patients [Brown et al. 2012]. Residual tumoral viability at imaging post-embolization is the primary criterion used in determining the need to re-treat. TACE is frequently iterative – up to 65-75% of tumors will demonstrate residual blood flow and require repeat TACE or alternative treatments. The lack of efficacy on the initial treatment may be due to reaching premature stasis because of slow flow conditions, vasospasm limiting delivery, or redistribution of flow to the lesion from an alternative hepatic branch after primary branch occlusion.

Contrast-enhanced magnetic resonance imaging (CE-MRI) is the standard imaging modality used to assess response to TACE by evaluating residual blood flow within the tumor [Brown et al. 2012; Hammerstingl et al. 2008; Akai et al. 2011]. The Society of Interventional Radiology guidelines recommend imaging follow-up four weeks post treatment [Brown et al. 2012]. A lack of arterial phase enhancement is used to indicate the lack of residual tumoral blood flow due to complete embolization and tumor necrosis. This one month time point has been adopted based on experience with the use of Lipiodol and on follow-up with contrast-enhanced computed tomography (CECT) scans; the non-tumor bearing liver requires 3-4 weeks to eliminate the Lipiodol by Kupffer cell phagocytosis [Brown et al. 2012]. In CE-MRI, the use of low molecular weight and water soluble contrast agents renders it difficult to differentiate granulation tissue and residual tumor perfusion and to differentiate peripheral viable tumors from inflammatory peritumoral infiltration if scanned within four weeks of treatment [Yan et al. 2002]. Differentiation between viable tumor and inflammation can be made in some cases by evaluating enhancement washout kinetics. Nevertheless, the cost of imaging and difficulty of inflammation in many cases has resulted in follow-up imaging recommendation to remain at 1 month [Brown et al. 2012]. CECT is used in patients in whom MRI is contraindicated. Confluent, dense Lipiodol uptake within treated tumors correlates with complete tumor necrosis, but may mask some residual tumor perfusion on CECT [Imaeda et al. 1993; Ito et al. 1995]. Following imaging, TACE or alternative treatment is repeated until a complete lack of arterial enhancement is achieved, after which tumoral response (evaluated by modified response evaluation criteria in solid tumors (mRECIST)) is assessed at 3-6 month intervals.

While follow-up imaging standards are well established, several limitations exist. CE-MRI may not be feasible in patients with metallic implants, renal contraindications (glomerular filtration rates <30 mL/min/1.73 m² [Shellock and Spinazzi 2008]), the inability to breath hold or claustrophobia. CECT may be contraindicated in patients with severe allergy to iodinated contrast and renal impairment. The radiation exposure associated with repeated CT imaging (particularly in patients who undergo multiple TACE treatments) also renders CT a suboptimal imaging modality. Additionally, the costs and limited availability

of CE-MRI or CT may place a significant, unnecessary burden on the health system. A final limitation of existing imaging techniques is the required delay between treatment and imaging to evaluate response due to the inherent properties of the MRI/CT contrast media and the presence of Lipiodol in the background liver. Consequently, time to retreatment is prolonged and in patients where TACE is used to downstage disease, a decision regarding transplantation is delayed. Phase II efficacy and pharmacokinetic studies show liver function generally returns to normal within 7 days after DEB-TACE [Varela et al. 2007]; thus, retreatment before the standard 5-7 weeks is feasible. In addition, retreatment by ablation may also be performed earlier with advanced screening of effective embolization. An imaging test that provides earlier identification of tumoral blood flow after TACE would shorten the time between treatments and potentially improve patient outcomes. Once tumor avascularity is confirmed, patients could resume standardized CE-MRI/CT long term follow-up protocols.

We propose the use of contrast-enhanced ultrasound (CEUS) as a potential solution. Ultrasound contrast agents are composed of a gas microbubble, encapsulated by an outer protein or lipid shell [Goldberg et al. 2001]. Ultrasound imaging is portable, provides real time imaging, uses non-ionizing radiation, is less expensive than CT/MRI, and is more readily available than MRI/CT imaging [Lewin 2004]. While CEUS is currently only approved by the FDA for echocardiography, the technique represents the primary imaging modality for numerous hepatic and vascular applications worldwide [Claudon et al. 2012; Bouakaz and de Jong, 2007]. CEUS also offers significant cost savings relative to CE-MRI/CT in the characterization of liver lesions [Westwood et al. 2013]. After intravenous injection, ultrasound contrast agents permeate throughout the blood supply, including the neovascular tumor supply, thereby providing enhancement of the tumor vasculature [Eisenbrey and Forsberg 2010]. The diameter of the contrast microbubbles (1-8 μm) enables them to pass through the pulmonary capillaries, but still restricts them to the vasculature, making them excellent intravascular blood pool agents [Correas et al. 2001]. Unlike the contrast agents used in MRI/CT, ultrasound contrast agents are not nephrotoxic and have no renal contraindications, making them an exceptionally safe imaging test. The presence of Lipiodol in the lesion does not interfere with ultrasound imaging. Unlike CT or MRI contrast agents, ultrasound contrast agents are completely confined to the vascular space and thus enable clear visualization of the tumor vasculature, despite any presence of inflammation. Finally, the higher temporal resolution of ultrasound avoids motion artifacts in patients with poor breath holding capability. Thus, CEUS is an attractive imaging alternative for identifying residual vascularity post-TACE.

Recent technological advances in the field of medical ultrasound are expected to aid in these goals. Contrast-specific imaging techniques can isolate nonlinear microbubble signals from the surrounding tissue

to enhance visualization of vascularity [Philips 2004; Eisenbrey 2011a]. Additionally, the recent implementation of real-time 3D (i.e. 4D) transducers enables volumetric imaging at acceptable acquisition rates (2-6 volumes/second for 4D ultrasound vs. 20+ frames/ second for 2D ultrasound imaging) and image quality [Eisenbrey et al. 2012]. Finally, blood flow kinetics in tissue can be quantified using dynamic-CEUS (D-CEUS) or parametric imaging [Eisenbrey et al. 2011b] and these techniques have also been applied using 4D CEUS to enhance quantification of blood flow within a tissue volume [Sridharan et al. 2012].

Pilot studies by our groups suggest that 2D CEUS provides accurate and earlier identification of residual tumoral blood flow (relative to current imaging guidelines [Brown et al. 2012]) in TACE patients treated with Lipiodol [Kono et al. 2007] and drug-eluting beads [Shaw et al. 2014]. Importantly, results from our CEUS study with c-TACE also indicate that CEUS may be more accurate than CE-MRI/CT at 1 month for evaluating residual blood flow [Kono et al. 2007]. Other studies evaluating the use of 2D CEUS as a follow-up imaging tool for TACE therapy reported that the lack of tumor enhancement correlates well with an avascular treatment response [Vallone et al. 2003; Salvaggio et al. 2010; Moschouris et al. 2010; Takizawa et al. 2013]. Xu et al. [2010] used static volumetric (3D) CEUS to monitor HCC response to local therapy and found the addition of volumetric ultrasound provided improved diagnostic confidence relative to 2D CEUS. Nevertheless, in this study, static 3D CEUS was used (potentially missing important dynamic volumetric data), only 12 patients underwent TACE therapy (and the majority of these TACE cases were treated in combination with ablation), effects of follow-up times were not investigated, and follow-up time ranged from 10 minutes to 28 months.

Sufficient data relating to a contrast agent approved for use in the USA, the use of 4D volumetric CEUS, the influence of reader or operator dependence, or the effect of follow-up time of CEUS for evaluating TACE therapy are not available. Additionally, D-CEUS remains a relatively unexplored option for characterizing treatment response to TACE therapy and may offer further improvements in diagnostic accuracy. Such findings could provide a safe, cost-effective and readily available follow-up imaging alternative, while also potentially improving patient outcomes by providing earlier and more accurate identification of patients requiring re-treatment. We propose a multi-center clinical trial to determine the sensitivity and specificity of 2D and 4D CEUS for evaluating TACE 1-2 weeks and 1 month post-treatment.

The proposed agent for the current study, Definity is a sterile non-pyrogenic suspension of liposome-encapsulated perfluoropropane microbubbles [Goldberg et al 2001; Miller & Nanda 2004]. The contrast agent is composed of a blend of three phospholipids contained in a matrix of sodium chloride, propylene glycol, and glycerin in water. The contrast agent is supplied in a vial that contains the phospholipids and

perfluoropropane gas. The microbubble agent is supplied in a standard-size 2 ml vial and is prepared by shaking the vial with the aid of a shaking device (Vialmix: ESPE, Seefeld, Germany).

Definity is currently only approved for use in echocardiography. The agent will be used as an off-label indication for this study. We intend to apply for an FDA investigator-instantiated IND for the off-label usage of Definity for the evaluation of chemoembolization.

Definity Clinical Safety

Definity is well tolerated and has been used extensively in echocardiography applications [Goldberg et al 2001]. In pre-market clinical trials, Definity was administered to 1716 patients. In these patients 269 (8.4%) reported at least one adverse event. Of these events, 26 were classified as serious including 19 (1.1%) patients experiencing serious cardiopulmonary symptoms including eight deaths. The deaths occurred several days after activated Definity administration and appear to be related to the course of underlying disease. Of the 11 other serious adverse events, which appeared within days of the drug administration (2-15 days), all appeared to be a progression of underlying cardiac and non-cardiac disease. However, a role for Definity in the initiation or course of these adverse events can not be ruled out. Of the reported adverse reactions following the use of Definity the most frequently reported were headache (2.3%), back and renal pain (2.1%), flushing (1.1%), and nausea (1.0%). Additional risks associated with the contrast material are described in the attached Definity Product insert (Appendix B). All of the non-serious reported side effects have been transient, usually lasting only a few minutes.

Table 1.

Selected Adverse Events Reported in $\geq 0.5\%$ of the Subjects who Received Definity in Controlled Clinical Studies

No. of Patients Exposed to Definity	1716	
No. of Patients Reporting an Adverse Event	269	(8.8%)
Central and peripheral nervous system	54	(3.2%)
Headache	40	(2.3%)
Dizziness	11	(0.6%)
Body as a Whole	41	(2.4%)
Back/Renal Pain	20	(1.2%)
Chest Pain	13	(0.8%)
Digestive System	31	(1.8%)
Nausea	17	(1.0%)
Vascular (extracardiac) disorders	19	(1.1%)
Flushing	19	(1.1%)
Application Site Disorders	11	(0.6%)
Injection Site Reactions	11	(0.6%)

Additional information concerning pre-clinical and clinical experience with Definity, including the dosing levels and reported subject complaints, can be found in the Definity Package Insert that is included as Appendix B.

